7.5. Data Sources

7.5.1. Deutsches Hämophileregister

This study will leverage data from the DHR, a clinical German registry maintained by the Paul-Ehrlich-Institute in cooperation with the Gesellschaft für Thrombose- und Hämostaseforschung e. V. (GTH), the Deutsche Hämophiliegesellschaft zur Bekämpfung von Blutungskrankheiten e. V. (DHG) and the Interessengemeinschaft Hämophiler e. V. (IGH).²⁴ It is a registry for medical research and quality assurance in the care of persons with hemophilia A, hemophilia B, von Willebrand syndrome or other coagulation factor deficiencies. Medical data of individuals with hemostasis disorders are compiled in the DHR. It has been in operation since December 2008. About 130 institutions report data from a total of almost 8,500 affected persons every year.²⁵

As a clinical patient registry, the DHR represents a systematic collection of data, i.e., standardized medical documentation, which makes data more comparable and thus evaluable in order to answer questions relevant to practice. As hemophilia is a rare disease, a registry is of particular importance: large-scale studies are often difficult to conduct in this field, as there are simply not enough patients to make reliable statements. Therefore, the strength of a registry lies in the possibility of long-term observation of the disease and its treatment in order to be able to draw meaningful conclusions.

The legislator has recognized this and, with an extension of the Transfusion Act (Transfusionsgesetz, TFG), has given the DHR a special status with a legal basis. Data collection in the DHR is now mandatory and all treating physicians are obliged to inform their patients about participation in the DHR.

Individuals consent to their data being included in the DHR. Baseline information is collected including demographic characteristics and baseline history. Other information including treatments, clinical outcome assessments (COAs), and bleeding events are expected to be recorded at least two times per year. For individuals who do not consent, minimal anonymous data is collected. As of 2018, there were 4,240 individuals with HA included in the DHR, 2,583 of whom had severe HA. This represents 104% of expected cases of severe HA in Germany, using an average prevalence of 6.0 cases of severe HA per 100,000 males and a German population of 83 million.^{1, 26}

7.6. Study Sample Size

The primary goal of HA treatment is to reduce the bleeding rate or to achieve freedom from bleeding. As an approximation of the appropriate number of cases for the data collection accompanying the application, the Institute for Quality and Efficiency in Health Care (IQWiG) conducted the sample size calculation based on ABR for treated bleeds. Evaluation of the ABR is performed using a negative binomial model.

The formula for The sample size calculation is as follows:

$$N_1 \geq \frac{(z_\alpha \sqrt{V_0} + z_\beta \sqrt{V_1})^2}{(\log(R_0) - \log(\lambda_2/\lambda_1))^2}$$

$$N_2 = \theta N_1$$

Where:

$$V_1 = \frac{1}{\mu_t} \left(\frac{1}{\lambda_1} + \frac{1}{\theta \lambda_2} \right) + \frac{(1 + \theta)\varphi}{\theta}$$

V_0 is computed using the fixed marginal total method, the 2nd method recommended by Zhu et al.:²⁷

$$V_{02} = \frac{(1 + R_0\theta)^2}{\mu_t R_0 \theta (\lambda_1 + \theta \lambda_2)} + \frac{(1 + \theta)\varphi}{\theta}$$

N_1 is the sample size for control, N_2 is the sample size for intervention. $\theta = \frac{N_2}{N_1}$, which is the sample size ratio; R_0 is the superiority margin ratio at the null hypothesis. In this case, R_0 is <1 since higher rates are worse. λ_1 is the event rate in the control group, and λ_2 is the event rate in the intervention group. φ is the dispersion parameter, and μ_t is the average exposure time. z_α is the z-score at the significance level, z_β is the z-score at the power value.

When higher rates are worse, the superiority by a margin test hypotheses are

$$H_0: \frac{\lambda_2}{\lambda_1} \geq R_0 \quad \text{vs.} \quad H_1: \frac{\lambda_2}{\lambda_1} < R_0$$

Where $R_0 < 1$.

The relative effect measure is the incidence rate ratio of Roctavian over SoC, which can be tested against the shifted null hypothesis of 0.5, assuming a significance level $\alpha = 2.5\%$ with a one-sided test, and power of at least 80%. Higher values for the ABR (parameter λ) stand for a worse outcome. Furthermore, a distribution of the Sample Roctavian vs. SoC of 1:5 is assumed (sample size ratio $\theta = 0.2$). Other required parameters are the Average Exposure Time ($u_t = 1$ year), the ABR for the SoC and Roctavian groups ($\lambda_{SoC} = 3$, $\lambda_{Roctavian} = 0.85$) and a value for the overdispersion ($\phi = 1.5$). This results in a total sample size of at least 397 participants (Roctavian Cohort $n = 67$, control Cohort $n = 330$).

Based on current estimates of participant enrollment, the study will be powered based on the ABR approach. The sample size calculation is based on a shifted null hypothesis of 0.5 to add robustness to the generated evidence. Applying and testing a lower shifted null hypothesis (e.g., 0.2) is not feasible to obtain from a physician's perspective and was not agreed upon in the initial sample size discussions with G-BA. In an oral hearing the physicians representing the Gesellschaft für Thrombose und Hämostasieforschung e. V. (GTH) and the Deutschen Gesellschaft für Hämatologie und Medizinische Onkologie e. V. (DGHO) estimated the available population for this study under 700 and only 50% were in single case reporting.²⁸

In addition to the shifted null hypothesis, propensity score methodology will be applied to this study design to account for uncertainty in the non-randomized design and ensure the study is more closely approximating randomization.

7.7. Data Management

All data for this study will be collected and stored in the DHR. Study site personnel is responsible for clinical data collection and data entry into the DHR. Validation of clinical data in the clinical database will be carried out via automated edit checks as well as manual checks raised by clinical research associates during on-site routine monitoring visits. Data fields in the DHR (described in sections 7.4.1, 7.4.2, and 7.4.3) are either mandatory to be entered into the registry per DHR practices or will be monitored (see section 8.1.2) to ensure completeness of data for analyses. In order to maximize the interpretability of interim analyses, study sites will be asked to enter data specifically for these analyses, which may fall outside of annual reporting at a site. Trained site monitors will provide support to participating sites to minimize the incidence of missing data through routine on-site

monitoring visits and remote routine monitoring visits, tailored to each site depending on the number of participants enrolled and data entry compliance into the DHR.

Furthermore, prior to each planned interim analysis reporting period, site monitors will perform on-site monitoring visits to ensure that all available data has been recorded into the DHR for enrolled participants only.

BioMarin will request data cuts from the DHR at specified intervals to assess data 18 months after the study start date and subsequent 18-month intervals for the duration of the study period. Note that the actual data cuts will be requested earlier so that interim reports can be completed as scheduled. These data cuts will be sent directly to [REDACTED] for analysis. All data are stored on secure servers and are auto-archived and password-protected for any future access requirements. Study documents are retained in a minimum of two secure locations and are only removed or deleted upon sponsor-written request.

7.7.1. Statistical Software

SAS® software (SAS Institute Inc., Cary, North Carolina, United States [US]) version 9.4 or higher will be used to manage the analytic datasets and conduct data analyses. The R survival package (version 3.2-13 or higher; R version 3.5.2) may be used to conduct weighted survival analysis and additional analyses.

7.7.2. Data Protection

Measures will be taken to ensure the privacy of subject data, including the use of subject numbers in the DHR. A list linking subject identification numbers with subject names and other personal information will be kept in a secure place, separate from the subjects' medical records. BioMarin will follow all applicable regulations and guidelines in the relevant locality, country, and/or region to protect the privacy of subject data.

Subjects are expected to have a consistent unique identifier based on a de-identified study center code and unique DHR number (e.g., participant at study center A may be identified as A-101). Any subject records or datasets that are transferred to the sponsor will contain the identifier only; subject names or any information which would make the subject identifiable will not be transferred. Study centers that participants are seen at will not be identifiable.

The subject must be informed that his/her personal study-related data will be used by the sponsor in accordance with local data protection law. The level of disclosure must also be explained to the subject, who will be required to give consent for their data to be used as described in the informed consent.

The subject must be informed that his/her medical records may be examined by Clinical Quality Assurance auditors or other authorized personnel appointed by the sponsor, by appropriate Institutional Review Board (IRB)/ Independent Ethics Committee (IEC) members, and by inspectors from regulatory authorities.

In the event of a data security breach, participating institutions, study vendors, and/or BioMarin will take appropriate action according to their local processes and report to appropriate regulatory agency(ies) according to applicable laws and regulations.

7.8. Propensity Score Methodology

Based on the prospective cohort study design, heterogeneity of covariates among the Roctavian and SoC Cohorts will be accounted for by propensity score methods. Considering the intended sample sizes as well as the primary question of interest (e.g., the benefit of Roctavian vs SoC), weighting

methodologies will be preferred and *a priori* the primary analyses will utilize inverse probability of treatment weighting (IPTW). IPTW will utilize all available data compared to matching approaches and estimate the average treatment effect (ATE). Sensitivity analyses will be performed using alternative methods. Propensity score matching (PSM) is planned to be utilized as the main sensitivity method *a priori*. As the primary analysis plans to utilize IPTW and the *a priori* sensitivity analysis is planned to be PSM, these methods have been discussed below in Sections 7.8.3.1 and 7.8.3.2.

7.8.1. Estimation of the Propensity Score

In the absence of randomized controlled trial data, propensity score methods are commonly used to account for heterogeneities in baseline covariates that may exist among multiple cohorts. In this section, the methodology of propensity score estimation is described.

Propensity scores will be calculated for participants in the Roctavian and the SoC Cohorts to balance covariates and obtain an unbiased estimate of the treatment effect. Propensity score is the probability of each subject being assigned to Roctavian, conditional on the key prognostic factors included in the model. Propensity scores will be estimated by fitting a multivariable logistic regression model, using backwards stepwise regression, that includes the key prognostic factors (described in Section 7.8.2) as covariates. The Cohort indicator (Roctavian Cohort (Y=1) or SoC Cohort(Y=0)) will be used as the dependent variables. The logistic regression model is mathematically expressed as

$$\text{logit}(\text{Pr}(Y = 1)) = X'\beta,$$

where $\text{logit}(\cdot)$ represents the logit function and X represents the vector of prognostic factors. After the model fit, propensity scores will be generated for all participants without missing values in any prognostic factors included in the model for subsequent analyses. The logit transformed propensity score (LTPS) is considered associated with preferred statistical properties (e.g., approximately normally distributed) over the raw propensity score and is therefore often used in applications of PSM methods.

All variables listed in Table 6 will be assessed as prespecified candidate covariates for inclusion in the propensity score models. Potential variables for inclusion in the propensity score have been identified based upon variables from a literature review of factors associated with bleeding, previous propensity score development for a comparison of Roctavian to FVIII prophylaxis based on studies that were part of the Roctavian clinical development,^{29, 30} and clinical input from health care practitioners (HCPs) in Germany managing PwSHA. Statistical relationships between potential variables and treatment cohorts for the study data, along with clinical input on variables to include regardless of statistical relationship, will be utilized to select variables included in the propensity score.

For each logistic regression model, parameter estimates of the covariates and their standard errors, odds ratio (OR) and their two-sided Wald 95% confidence interval (CI) will be presented for continuous variables and the non-reference levels of categorical variables. P-values for each corresponding OR and for each parameter will be presented. The number of participants in each category level will be presented, as well as the total number of participants with non-missing data for each continuous variable (which by construction will equal the number of participants in the model).

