10.3.3. Estimation of the Propensity Score

A PS is the probability of receiving treatment given an observed set of known covariates, which can be used to balance covariate values between the treated and control participants to obtain an unbiased estimate of treatment effect.

The PS in this analysis represents the probability of participants being in the Roctavian cohort given the observed set of baseline participant characteristics. This will be calculated using a logistic regression model predicting treatment assignment from baseline characteristics.

Propensity scores will be developed based on baseline characteristics of the study cohorts (see Section 10.2) described in Table 3 and Table 4. Potential variables for inclusion in the PS have been identified based upon variables from a literature review of factors associated with bleeding, previous PS development for a comparison of Roctavian to FVIII prophylaxis based on studies that were part of the Roctavian clinical development (Liu 2022; Oldenburg 2024; see Appendices for further details), and clinical input from health care practitioners

(HCPs) in Germany managing PwSHA. Statistical relationships between potential variables and treatment cohort (as defined in the SAP) for the study data, along with clinical input on variables to include regardless of statistical relationship will be utilized to select variables included in the propensity score.

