[Table 9](#) outlines the potential variables to include in the PS based on the comprehensive literature review, expert physician input, and prior comparative Roctavian versus FVIII prophylaxis studies PS development along with considerations for inclusion based on clinical relevance, potential statistical associations, and anticipated correlations between variables. Prior bleeding history, ABR (12 months prior to index date), will be included in the PS regardless of statistical significance due to clinical significance based on feedback from German physicians. See the SAP for further information regarding operationalization of the variables for PS assessment in the SAP.

Table 9: List of potential variables for inclusion in PS

Variable	Literature review	From previous PS work	Clinical expert opinion	Considerations
Baseline/prior bleeding history (eg, ABR)	✓	✓	✓	Include regardless of statistical association, based on clinical relevance
Baseline FVIII utilization	✓	✓	✓	Include based on statistical association and correlation with other variables (eg, baseline/prior bleeding history and baseline prophylaxis class)
Baseline prophylaxis class (FVIII vs. emicizumab)	✓	✓	✓	Include based on statistical association and correlation with other variables (eg, baseline/prior bleeding history and FVIII utilization)
Age	✓	✓	✓	Include based on statistical association
Height, Weight and/or BMI	✓	✓	✓	Include based on statistical association
Baseline von Willebrand factor (IU/mL)	✓	X	✓	Include based on statistical association
Number of target joints	✓	✓	X	To be considered depending on statistical association and correlation with other variables (eg, baseline/prior bleeding history and joint health score)
Joint health (eg, baseline/prior HJHS)	X	X	✓	To be considered depending on statistical association and correlation with other variables (eg, baseline/prior bleeding history and number of target joints)
Baseline/prior type of bleeds	X	X	✓	To be considered depending on statistical association and correlation with other variables (eg, baseline/prior bleeding history and target joints)
Geography (HTC/site/region/country)	✓	✓	X	Site to be considered depending on statistical association and correlation with other variables
Prophylaxis class switching (eg, SHL/PD to EHL/emicizumab)	✓	✓	X	To be considered depending on statistical association and correlation with other variables

Variable	Literature review	From previous PS work	Clinical expert opinion	Considerations

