7.8.2.3. Baseline Comparison of Groups for Propensity Score Development

Participant characteristics will be presented for all baseline variables described in Table 3 and Table 4, along with tests for difference using appropriate statistical testing; Welch's t-test for continuous variables, and the Chi-square test for categorical variables.

SMD will be calculated for continuous and categorical variables. SMD represents the most commonly used statistic to examine the balance of covariate distribution between groups, with a value greater than 0.1 indicating some imbalance between groups and > 0.25 indicating poor imbalance, where the model should either be improved or rejected in favor of an alternative model.³³ If imbalance of > 0.25 remains, the propensity score model will be refined by adding additional covariates, adding interaction terms and/or conducting appropriate transformation of the covariates (squared, log, etc.). Any covariates that remain imbalanced (SMD>0.25) after further refinement of the propensity score model (due to lack of propensity score model convergence) will be removed from the propensity score model and included/adjusted for in the regression model (for model-based analyses – i.e., bleeding events) to estimate the ATE on the outcome.

After propensity score methods have been applied, tabulations will be repeated with p-values and SMDs re-calculated to investigate any meaningful differences remaining after propensity score-adjustment, both in the characteristics included in the propensity scoring, and also those not included. Although all baseline characteristics will be presented for completeness, the balance of the variables included within the propensity score models will be the focus due to the importance assigned to these characteristics.

In accordance with guidance that model-evaluation tools of the logistic regression are secondary to the balancing of participant characteristics,^{34, 35} additional analyses will also be performed with the omission of highly correlated variables. Collinearity among covariates that are used to generate weighting from the IPTW method will be assessed by the variance inflation factor (VIF) and

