more similar Roctavian and SoC Cohorts. Other clinically significant prognostic factors or covariates that remain imbalanced after propensity score adjustment will be included in the model as well. Regression coefficients, corresponding 95% CIs and p-values will be reported for all explanatory variables included in the model. The estimated rate ratio (ABR in Roctavian Cohort / ABR in SoC Cohort) generated from the IPTW weighted negative binomial model will be tested against the shifted null hypothesis of 0.5. For an alpha=0.025 test, the shifted null hypothesis is rejected if the upper boundary of the two-sided 95% CI for the rate ratio is less than the null hypothesis 0.5. The CI of the estimated rate ratio will be calculated using the Wald method.²⁷

Given some participants may have no treated bleeds based on prior literature,⁴⁶ a two-part zero-inflated negative binomial model will also be considered. If the negative binomial model does not converge,⁴⁷ or if the AIC in the model accounting for zero-inflation is lower, then the zero-inflation negative binomial model will become the primary objective analytic model, as lower AIC indicates a better fit. For the zero-inflated negative binomial model, first the model will be fit for a binary outcome whether a participant had a treated bleed during the outcome assessment period, and then an ABR count outcome for treated bleeds among participants who had at least one treated bleed during the outcome assessment period (excluding participants with zero bleeds) will be fit. Finally, the unconditional ABR estimates for treated bleed will be calculated by multiplying the estimated conditional ABR from the count model by the probability of having a treated bleed estimated from the binary model for both the Roctavian and SoC Cohorts.

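### Apart from prior ABR, known bleeding predictors enter the propensity score by backward selection on association with treatment, a weak screen with 67 treated participants, and the fallbacks leave SMDs of 0.1 to 0.25 without a fixed rule

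*Protocol*

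**What the plan says.** SAP 7.8.1 describes the score model: "Propensity scores will be estimated by fitting a multivariable logistic regression model, using backwards stepwise regression, that includes the key prognostic factors". The outcome of that model is the cohort indicator. Protocol 10.3.3 names the selection basis as "Statistical relationships between potential variables and treatment cohort (as defined in the SAP) for the study data", together with clinical input on variables to keep regardless of it. Protocol Table 9 and SAP Table 6 apply this row by row. Prior bleeding history is included whatever the association. Baseline FVIII use and prophylaxis class carry the rule "Include based on statistical association and correlation with other variables". Age, body size and von Willebrand factor (VWF) enter on statistical association. Target joints and HJHS are considered on the same basis. No retention p-value or criterion is stated.

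Two fallbacks follow. SAP 7.8.2.3 re-checks balance after weighting, both for variables in the score and for those outside it, with the former as the focus: "If imbalance of > 0.25 remains, the propensity score model will be refined by adding additional covariates". Covariates still above 0.25 after refinement move to the outcome regression. SAP 7.9.3 separately says that clinically significant prognostic factors, or covariates still imbalanced, will be added to the primary model, and it gives no cut-off.

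On what counts as imbalance, Protocol 10.3.4.1 uses an SMD above 0.1. SAP 7.8.2.3 calls that some imbalance and reserves action for values above 0.25.

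Finally, the note under shell Table 4 in SAP Annex 12.1 says the covariates will be fixed before data collection begins. Selection on the study data cannot satisfy that.

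**The concern.** A confounder has to be related to both treatment and outcome. Most candidates are listed because the literature review, earlier propensity score work or clinicians link them to bleeding, so the outcome side is largely argued already. The plan then makes retention depend on a significance test of the treatment side. With a small treated group, a non-significant test is weak evidence of balance.

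The stake is residual confounding in the primary rate ratio. If Roctavian recipients happen to have a milder profile on several predictors, modest imbalances left outside the score would push the ratio towards Roctavian. If they have a more severe profile, the bias would run the other way. The documents say that the characteristics of both cohorts are not yet known (Protocol 10.3.5 and 10.5), so neither direction can be assumed. That argues for fixing the adjustment set now.

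**Working it through.** **Inputs.** SAP 7.6: "This results in a total sample size of at least 397 participants", that is 67 Roctavian and 330 SoC; "which can be tested against the shifted null hypothesis of 0.5"; one-sided alpha 2.5%, "with a one-sided test, and power of at least 80" per cent; rates 3 and 0.85; dispersion 1.5; exposure 1 year; θ = 0.2. SAP 7.9.3: "For an alpha=0.025 test, the shifted null hypothesis is rejected if the upper boundary of the two-sided 95% CI" lies below 0.5.

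**Step 1: reproduce the sample size.**
- V1 = 1/3 + 1/(0.2 × 0.85) + 1.2 × 1.5/0.2 = 0.333 + 5.882 + 9 = 15.216
- V0 = (1 + 0.5 × 0.2)² / [0.5 × 0.2 × (3 + 0.2 × 0.85)] + 9 = 1.21/0.317 + 9 = 12.817
- N1 = (1.960 × √12.817 + 0.842 × √15.216)² / (ln 0.5 − ln 0.2833)² = 328.8

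This gives 329 SoC and 66 Roctavian, 395 in total against the stated 397. The two agree closely, and power at 330/67 is 80.6%. The group sizes can be relied on.

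**Step 2: how large must an observed imbalance be to test as significant?** For one covariate, SE(SMD) ≈ √(1/67 + 1/330) = 0.134.
- p<0.05: 1.960 × 0.134 = 0.263
- p<0.20: 1.282 × 0.134 = 0.172

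**Step 3: chance that a true imbalance is non-significant.** This is approximately Φ((cut-off − true SMD)/0.134). For a true SMD of 0.25 at p<0.05: Φ((0.263 − 0.25)/0.134) = Φ(0.09) ≈ 0.54.

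| True SMD | p<0.05 | p<0.10 | p<0.157 (AIC-like) | p<0.20 |
|---|---|---|---|---|
| 0.10 | 89% | 82% | 75% | 70% |
| 0.20 | 68% | 56% | 47% | 42% |
| 0.25 | 54% | 41% | 33% | 28% |

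The retention level is an assumption. SAP 7.9 uses 0.05 as its general significance level but does not tie it to the stepwise procedure. Simulated backward selection with 12 independent candidates, one of them forced (200 runs per setting, Monte Carlo error about 3.5 points), dropped a covariate with SMD 0.25 in 54%, 46%, 33% and 27% of runs at the four levels. The one-covariate figures are therefore a fair guide.

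**Step 4: does the trigger at 0.25 recover what selection drops?** At p<0.05 selection already keeps observed SMDs above 0.263, so the trigger adds only the band from 0.25 to 0.263. For a true SMD of 0.25 that is Φ(0.09) − Φ(0) ≈ 0.04, or 4 of the 54 percentage points. At p<0.20 the selection cut-off (0.17) already lies below the trigger, so it adds essentially nothing. This treats the weighted SMD of an excluded variable as close to its unweighted value.

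**Step 5: what the other safeguards fix.** The clinical override names prior ABR and nothing else. SAP 7.8.2.3 sends a covariate to the outcome model only above 0.25. SAP 7.9.3 could be read as reaching lower, but it does not say at what value.

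**The case against.** The strongest reply is that the score is not the only adjustment. Clinical input can add variables (SAP 7.8.1), variables outside the score are re-checked (SAP 7.8.2.3), and SAP 7.9.3 adds clinically significant or still imbalanced covariates to the primary model. Read with a cut-off of 0.1, the last of these largely closes the gap. In a simulation with seven bleeding predictors, each imbalanced by 0.2 in Roctavian's favour, with rate ratio 1.2 per SD and true ratio 0.5, stepwise selection plus the 0.25 trigger gave a mean ratio of 0.44. Adding outcome-model adjustment above 0.1 gave 0.48, the same as forcing all seven in. This stands, but it depends on a cut-off that SAP 7.9.3 does not state and SAP 7.8.2.3 contradicts.

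Three stronger readings are tempting and are not supported.
- **That variables enter only if statistically associated, and non-significance is taken as balance.** The override, the re-check and the outcome-model adjustment say otherwise.
- **That the primary test has a particular inflated false-positive rate.** Across simulated scenarios the excess of stepwise over forced inclusion ran from nil to about 5 percentage points. The larger values need several imbalances in the same direction, unrelated to prior ABR. When the predictors also drove prior ABR, which is forced in, the two approaches did not differ.
- **That the rule favours variables such as site that predict treatment only.** Both tables credit geography to the bleeding literature review, and Protocol 10.5 links site to management and recording practice.

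Two cautions also stand. Of the 22 rows in SAP Table 6, 18 are not ruled out, or 67/18 ≈ 3.7 treated participants per row, so some reduction is needed. And with SE 0.134, about 46% of truly comparable covariates would exceed 0.1 before weighting, so a 0.1 rule across every candidate would fire constantly.

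**Conclusion.** The point holds as a design weakness that is cheap to remove. Adjustment for known bleeding predictors other than prior ABR rests on a screen that misses a true SMD of 0.25 about 54% of the time at an assumed p<0.05 and about 28% at p<0.20. The refinement trigger recovers almost none of these misses, and the remaining safeguard has two different scopes in two sections. Imbalances of 0.1 to 0.25 may stay unadjusted; the documents do not show that they will. The size and direction of any bias are unknown until the cohorts are observed. Selection on study data also conflicts with the shell note that covariates are settled before data collection.

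**What to change.** 1. In SAP 7.8.1, and in SAP Table 6 and Protocol Table 9, replace backward stepwise selection with a short prespecified set forced into the score. A suitable set from the existing candidates is prior ABR, baseline FVIII use, prophylaxis class, age, BMI, number of target joints, VWF and, on clinical input, HJHS (the tables credit it to expert opinion only).
2. Drop a core variable only under rules the SAP already has: the collinearity rule in 7.8.2.3 or more than 40% missing in 7.9.5.1.
3. Align SAP 7.8.2.3 with 7.9.3: any core variable with weighted SMD above 0.1 is adjusted in the outcome model. Limiting this to the core set avoids the constant triggering noted above.

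This also makes the shell note true. The cost is wording, and eight covariates on 67 treated participants (67/8 ≈ 8.4 each). In simulation the SD of the log rate ratio rose from 0.25 to 0.27 in one set of runs and from 0.27 to 0.29 in another, so a standard error roughly 5 to 10% wider should be expected.
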